Study Protocol

External validation of EPIC's Risk of Unplanned Readmission model, the LACE+ index and SQLape[®] as predictors of unplanned hospital readmissions: A monocentric, retrospective, diagnostic cohort study in Switzerland

Project Leader & Corresponding contact (main author)	[name], M.A. HSG Research Project Manager & Advanced Analytics Analyst Lucerne Cantonal Hospital, Staff Medicine [name] E-Mail: [contact] [contact]
Health Economist, supervisor (co-author)	[name]. [name] Professor of Health Economics, Director Center for Health, Policy and Economics University of Lucerne [name]
Clinical Supervisor (co-author)	Dr.med. [name], [name] Head of Medical Staff, Co-Head Physician Anesthesia Lucerne Cantonal Hospital [name]
Quality Management Supervisor (co-author)	Dr. med. [name] General Manager DRG und Q&R-Management Lucerne Cantonal Hospital [name]

Research plan, Version and date 18.02.2020, V4.0

CONTENT

ABSTRACT
INTRODUCTION
RATIONALE & OBJECTIVES
METHODS
Study design & study sites
Participants
Predictors
Outcome(s)
Sample size
Data collection
Missing data8
Statistical analysis
Risk groups
Development vs. validation
Reporting10
Limitations
Other information
Supplementary information
Funding10
REFERENCES

ABSTRACT

Introduction: Readmissions after an acute care hospitalization are relatively common, costly to the health care system, and are associated with significant burden for patients. As one way to reduce costs and simultaneously improve quality of care, hospital readmissions receive increasing interest from policy makers. It is only relatively recently that strategies were developed with the specific aim of reducing unplanned readmissions by applying prediction models. EPIC's Risk of Unplanned Readmission model, developed in 2015 for the U.S. acute care hospital setting, promises superior calibration and discriminatory abilities. However, its routine application in the Swiss hospital setting requires external validation first. Therefore, the main objective of this study is to externally validate the EPIC's Risk of Unplanned Readmission model, LACE+ index and SQLape® model as predictors of unplanned hospital readmissions.

Methods: For this reason, a monocentric, retrospective, diagnostic cohort study will be conducted. The study will include inpatients, who were hospitalized between the 1st of January 2018 and the 31st of December 2019 in the Lucerne Cantonal hospital in Switzerland. Cases will be inpatients that experienced an unplanned (all-cause) readmission within 18 or 30 days after the index discharge. The control group will consist of individuals who had no unscheduled readmission.

For external validation, discrimination of the scores under investigation will be assessed by calculating the area under the receiver operating characteristics curves (AUC). For calibration, the Hosmer-Lemeshow goodness-of-fit test will be graphically illustrated by plotting the predicted outcomes by decile against the observations. Other performance measures to be estimated will include the Brier Score, Net Reclassification Improvement (NRI) and the Net Benefit (NB). All patient data will be retrieved from electronic clinical data bases.

Discussion

This is a presentation of the study protocol only. Results and discussion will be published after completion of this study.

Others

The study protocol was approved by the Ethics Committee Northwest- and Central Switzerland (ID:2019-01861) and will be registered on ClinicalTrials.gov.

INTRODUCTION

Readmissions after an acute care hospitalization are relatively common, costly to the health care system and are associated with significant burden for patients (1-5). A readmission increases the risk of dependence and functional or psychosocial decline [5]. Moreover, a readmission increases the risk of decompensation of other comorbid conditions, thus increasing the frailty of elderly patients [6].

The belief that readmission rates are a valid indicator to assess quality of care has led to their inclusion in hospital quality surveillance (6, 7). In September 2018, the Swiss National Association for Quality Development in Hospitals and Clinics (ANQ) reported its most recent findings. Accordingly, based on 2016 figures, the number of Swiss hospitals that reported more readmissions, as expected according to their patient mix, has more than doubled. In total, 47 out of 145 hospitals reported rates (observed/expected) outside the norm, i.e. significantly higher than 1 (8). This increase (+3.3%) in observed unplanned readmissions has been ongoing since 2011 and is proving to be statistically significant (9).

In the last few years, the observed increase in costs has been posing major challenges for the healthcare system. Healthcare costs in Switzerland have risen by a good third within the last decade (10). As one way to reduce costs and simultaneously improve quality of care, hospital readmissions receive increasing interest from policy makers. It is only relatively recently that policies were developed with the specific aim of reducing readmissions. In Switzerland, the readmission policy involves financial penalties, i.e., that patient records of the first admission and the relevant readmission are merged into a single case, if certain criteria are met. Consequently, hospitals receive only one DRG-based payment for both admissions (11). In result, and despite the fact that some readmissions cannot be avoided and the proportion of potentially avoidable readmissions (PARAs) remains debatable, health care organizations invest considerable resources into efforts to reduce hospital readmissions (12-14).

To most efficiently reduce readmissions, hospitals need to target effective discharge and postdischarge interventions at those who need them the most. One of the more recent strategies is the application of prediction models. As systematic reviews have shown, there are many models aimed at identifying those at greater risk of readmission (15, 16). The majority includes readily available predictors such as demographic and administrative data, comorbidities, laboratory, and medications (15). Among these models, the EPIC's Risk of Unplanned Readmission model, developed in 2015 for the U.S. acute care hospital setting, promises superior calibration and discriminatory abilities. The model was developed by EPIC Systems corporation based on data from 26 EPIC community member hospitals, including more than 275'000 inpatient hospital admission encounters to determine a patient's risk of unplanned readmission within 30 days of being discharged from an index admission.

RATIONALE & OBJECTIVES

Prediction models require internal and external validation. Whereas internal validations means testing the model in the population used to develop it, external validation means applying the model with its predictors and assigned weights, as estimated from the development study, to a new population; measuring the predictor and outcome values; and quantifying the model's predictive performance (calibration and discrimination).

Even though EPIC's Risk of Unplanned Readmission model was developed for the acute care hospital setting, variations in demographic features, disease prevalence and differences in test conditions (e.g. defining criteria of relevant readmissions, time frame of measurement) entail external validation prior to routine application in the Swiss acute care hospital setting.

For this reason, the main objective of this study is to externally validate EPIC's Risk of Unplanned Readmission model as i) a predictor of all-cause unplanned hospital readmissions within 30 days, ii) a predictor of unplanned readmissions within 18 days according to SwissDRG's specification, and to compare the model with the LACE+ index and the SQLape® readmission algorithm.

METHODS

Study design & study sites

This monocentric, retrospective, diagnostic cohort study will include all inpatients from the Lucerne Cantonal Hospital, which is the largest provider of basic and highly specialized healthcare services in Central Switzerland. This study is designed not to meet the criteria for research involving human subjects. The Ethics Committee Northwest- and Central Switzerland (EKNZ) will be informed and asked for an ethics waiver.

Participants

All inpatients, aged one year or older (max. 100 years), who were hospitalized either between the 1st of January 2018 and the 31st of December 2018, or between the 23rd of September and the 31st of December 2019 will be included. Cases will be inpatients that experienced (i) an unplanned readmission within 18 days according to SwissDRG's specifications; (ii) an unplanned all-cause readmission within 30 days after the index discharge. The control group will consist of individuals who had no unplanned readmission within the relevant days after the index discharge.

Exclusion criteria will be (a) admission/transfer from another psychiatric, rehabilitative or acute care ward from the same institution, (b) discharge destination other than the patient's home or (c) transfer to another acute care hospital, both being considered as treatment continuation; (d) foreign residence, (e) deceased before discharge, (f) discharged on admission day, (g) refusal of general consent, and (h) unknown patient residence or discharge destination.

For individuals with multiple readmissions during the study period, only the first readmission will be included into the analysis.

Predictors

The following paragraph provides a description of the predictive models to be evaluated. A distinct definition of the variables included is available from the corresponding author upon reasonable request. In advance, it needs to be mentioned, that the EPIC's Risk of Unplanned Readmission and the SQLape[®] Readmission Risk model are commercially distributed products. Implicitly, due to copyright issues, not all information about the predictors required to replicate this validation study were allowed to be disclosed in sufficient detail/at all. Replicating this study requires licensing.

EPIC's Risk of Unplanned Readmission model: The EPIC's Risk of Unplanned Readmission model is a logistic regression model that predicts the risk of all-cause unplanned readmissions within 30 days of the index hospital discharge. An all-cause unplanned readmission was defined according to the Centers for Medicare & Medicaid Services (CMS) Planned Readmission algorithm (version 2.1) (17).

The data set used for the development of the model included more than 275'000 hospital inpatient encounters from 26 different hospitals. Three of these hospitals were large academic medical centers (1000+ beds each), while the others were either smaller regional hospitals or community hospitals. All included sites were chosen from very distinct geographic regions in the US to ensure a population as diverse as possible. A selection by specialties/medical disciplines was not applied; all ages; any payer; and encounters for which patients leave the hospital against medical advice were included.

After feature selection, using a least absolute shrinkage and selection operator (LASSO) penalty, the final model consisted of 27 predictive parameters.

The internal and external validation of the model showed acceptable discrimination at predicting allcause unplanned readmission within 30 days post discharge with an area under the receiver operating characteristic curve (AUC of the ROC curve) ranging from 0.69 to 0.74.

LACE+: The LACE+ risk index is a point score derived from a logistic regression model, which was developed to predict the risk of 30-day post-discharge death or urgent readmission (18). It was developed and internally validated based on a large, randomly selected, population-based sample from Ontario, Canada in 2012. The development sample excluded patients who underwent same-day surgeries, psychiatric and obstetric admissions.

Backward feature selection was performed (with a significance level of $\alpha = 0.05$) and resulted in 11 significant covariates. The final point score ranges from -15 to 114, a score greater than 90 is considered with a high risk for unplanned readmission or death within 30 days after discharge. The internal validation of the 11-item index, excluding the Canada specific case-mix group (CMG) score,

showed reasonable discrimination with an AUC of the ROC curve of 0.743 for all-cause unplanned readmission, but poor calibration (H – L statistic 58.93, p < 0.0001).

SQLape®: The SQLape® readmission risk model (Striving for Quality Level and analyzing of patient expenditures), a computerized validated algorithm, was developed in 2002, in Switzerland (6). The SQLape® prediction model predicts unforeseen hospital readmission within 30 days after hospital discharge. The development sample consisted of 131'809 inpatient stays from 49 Swiss acute care hospitals, of which 12 hospitals were located in the French speaking part of Switzerland.

Healthy newborns, residents outside of Switzerland and elective surgical patients that could usually be performed as day surgery were excluded. After backward elimination was performed, the Poisson regression model consisted of six variables/SQLape variable groups. Of the beforementioned 131'809 inpatient stays, 66'069 were used for internal validation. The discrimination was measured by the Harrell's C statistic, which is also referred to as the estimated area under the Receiver Operating Characteristics (ROC) curve (AUC). A value of 0.72 showed reasonable discriminative ability.

Outcome(s)

The predicted outcome of all prediction models will be compared with the observed outcome. Both outcomes will be assessed retrospectively. The primary outcome will be the all-cause unplanned readmission to the same hospital within 30 days after the index hospital discharge. An unplanned readmission will be defined as an urgent readmission, i.e. not scheduled in advance and requires treatment within 12 hours.

The secondary outcome, as defined by the SwissDRG, will be the unplanned readmission to the same hospital, that resulted in a case merging (19). According to SwissDRG, patient records of the index admission and the nth readmission are merged into a single case if they fall into the same major diagnostic category (MDC), occurred within 18 days after the index/preceding hospital discharge date, and are not excluded from the case merging rule.

Sample size

Sample size calculations resulted in a aspired sample size of at least 1000 participants (500 cases and 500 controls) for each site. The proposed sample size is based upon precision. 500 cases and 500 controls will ensure that the half-width of a 95% confidence interval for sensitivity and specificity (using frequencies of predicted vs. actual outcome) does not exceed 5%; even for a point estimate of 50%, leading to the widest possible confidence interval, the half-width is supposed to remain slightly below 4.5%. This can be considered to be an appropriate target precision for the purpose of this study.

Data collection

Demographic and administrative data, medications, orders, International Classification of Disease (ICD) diagnosis codes, and biological data will be extracted in an anonymized manner from electronic patient records. Data covering the initial period will be retrieved from several different Information Systems (e.g. Dorner Lab. System, NEXUS/Medfolio etc.). Because of the introduction of a new Clinical Information System (CIS) in 2019, data covering the latter period of interest (23rd of September to 31st of December 2019) will be retrieved separately, i.e., from the new Clinical Information System from EPIC Systems corporation.

Missing data

Missing data required to compute the prediction models will be handled as following: Missing biological data (hemoglobin, sodium, calcium etc.) will be coded as normal values. Missing comorbidity and medication data will be considered as absence of the condition and no active medication, respectively. Missing order data (imaging, restraining, electrocardiogram) will be considered as an intervention not ordered. Lastly, missing records of utilization of health care resources (e.g. ED visits, scheduled future admissions etc.) will be considered as non-utilization.

Missing demographic or administrative data to describe patient's characteristics will result in the patient's exclusion from the analysis.

Statistical analysis

The EPIC's Risk of Unplanned Readmission model predictions and LACE+ scores will be calculated as the inverse of $1+e^{-(intercept+\beta^{1_*}x^1+\dots+\beta^{K_*}x^K)}$, where β will be the regression coefficient of each covariate (x), and K will be the total number of covariates. SQLape[®] readmission predictions will be automatically calculated by the plugin provided by the author.

To assess the performance, the traditional statistical approach is to quantify how close predictions are to the actual outcome. As overall performance measure, composing of discrimination and calibration, the Brier score will be calculated. Assessed separately, the discriminative ability will be measured using the Harrell's C-statistic, which, for binary outcomes, is identical to the area under the Receiver Operating Characteristic (ROC) curve (AUC). For calibration, the Hosmer-Lemeshow goodness-of-fit test will be graphically illustrated by plotting the predicted outcomes by decile against the observations. Furthermore, other performance measures to be estimated will include the Net Reclassification Improvement (NRI) and the Net Benefit (NB). All statistical analyses will be performed in R.

Risk groups

Risk groups will be established based on the recommendations by the developers of EPIC's Risk of Unplanned Readmission model, i.e., to use the organization's current readmission rate as baseline

risk and group as follows: "no risk = 0 – baseline", "low risk = baseline – 2 x baseline", "medium risk = 2 x baseline – 3 x baseline", "high risk = > 3 x baseline".

Development vs. validation

The differences in this validation study compared to the development studies are briefly summarized below:

EPIC's Risk Setting: U.S. multi-centric study, including more than 275'000 adult inpatients from 26 of different hospitals; the national readmission rate equals 10%-15% (20, 21) Unplanned Eligibility criteria: No relevant differences Readmission Outcome: The primary outcome was the unplanned readmission within 30 days of the index hospital discharge, defined according to the Centers for Medicare & Medicaid Services (CMS) **Planned Readmission algorithm Predictors:** ICD-10 codes vary slightly by country - diagnosis grouper will need modification; medication vendors and medicinal products can vary from country to country – ATC groups will need modification; less frequent ED use compared to the US - hence, the predictor might have a smaller effect (22, 23) LACE+ Setting: Multi-centric, Canadian study including medical and surgical adult inpatients who had been discharged to the community from an Ontario hospital; the study involved 500'000 randomly selected patients; the Canadian national readmission rate equals 9%-10% Eligibility criteria: All medical and surgical patients, excluding discharges to rehabilitation and long-term care facilities, patients who underwent same-day surgeries, psychiatric and obstetric and patients who were ineligible for health care coverage in Ontario. Outcome: The primary outcome was death or urgent readmission within 30 days of hospital discharge, the secondary outcome was only urgent readmission within 30 days of hospital discharge; variations in regard to the excluded procedures and diagnoses can be expected; the development sample covered, to some extent, external readmissions, i.e. patients being readmitted to another hospital - not considering external readmissions in the validation study can lead to over- or underestimation **Predictors:** The original study included the predictor variable case-mix group (CMG) to

capture important acute diagnoses and procedures performed during the index admission. Because the CMG score cannot be calculated for hospitals outside Canada the authors conducted a secondary analysis to determine the performance of the LACE+ index without the CMG score for the potential use in other countries. The performance was only slightly worse (AUC): 30-day death or urgent readmission resulted in 0.759 instead of 0.771, 30-day urgent readmission – 0.743 instead of 0.753; 30-day death – 0.860 instead of 0.883; ICD-10 codes vary slightly by country - diagnosis grouper will need modification; less frequent ED use compared to Canada – the predictor might have a smaller effect (23, 24)

 SQLape®
 Setting: No relevant differences

 Eligibility criteria: No relevant differences
 Outcome: The development study outcome was potentially avoidable readmissions within 30 days – compared to the outcome of this validation study, variations in regard to the excluded procedures and diagnoses can be expected

 Predictors: No relevant differences

Reporting

The study will follow the criteria from the transparent reporting of a multivariable prediction model for individual prognosis or diagnosis (TRIPOD) Initiative (25).

Limitations

Due to copyright issues, it will not be possible to describe the EPIC and SQLape[®] model in sufficient detail that would allow other researchers to replicate this study without licensing. Furthermore, this study will conduct its performance evaluation based on the assumption that if a specific parameter is not documented, it's true value is considered as uneventful. Compared to a prospective study design, where each required data input would be available as either positive or negative value, this study design is less powerful. Lastly, only readmissions to the same hospital will be considered, this can result in over-/underestimation of performance.

Other information

Supplementary information

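### Do the differing inclusion dates in the Abstract and in Participants leave the cohort, or the first-readmission rule, undecided?

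*Combined protocol and SAP*

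**What the plan says.** The Methods paragraph of the Abstract states: "The study will include inpatients, who were hospitalized between the 1st of January 2018 and the 31st of December 2019". It mentions no interruption.

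The Participants section includes inpatients "who were hospitalized either between the 1st of January 2018 and the 31st of December 2018, or between the 23rd of September" to 31 December 2019, so calendar 2018 plus a second window at the end of 2019. Data collection explains that second window by the introduction of a new clinical information system: "data covering the latter period of interest (23rd of September to 31st of December 2019) will be retrieved separately".

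Participants also sets a counting rule: "For individuals with multiple readmissions during the study period, only the first readmission will be included into the analysis". No section gives dates for the study period in that sentence.

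Outcome(s) defines the primary outcome as the "all-cause unplanned readmission to the same hospital within 30 days after the index hospital discharge". The secondary outcome is a SwissDRG case merging within 18 days. No calendar cut-off for retrieving readmissions is stated.

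**The concern.** Two sections of one current version name different inclusion periods, and the difference is large: 265 days, more than half the length of the two Participants windows combined.

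Preferring the Methods text for inclusion does not obviously settle the first-readmission rule. Take a patient readmitted in May 2019 and again in November 2019. If the study period is continuous, the May readmission is the first and the November one is dropped. If it is the two windows only, the November one counts. Two analysts with the same inclusion windows could then report different numbers of readmissions for late 2019, the only period drawn from the new system. Those counts enter the calibration display, which works by "plotting the predicted outcomes by decile against the observations".

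In addition, a 30-day outcome for a discharge in late December runs into January, and the plan does not say that readmissions are retrieved that far.

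**Working it through.** **1. Day counts (both end dates included)**
- Abstract: 1 January 2018 to 31 December 2019 = 730 days.
- Participants: 365 + 100 = 465 days.
- Difference: 730 − 465 = 265 days, exactly 1 January to 22 September 2019. 265/730 = 36.3%; 265/465 = 57.0%.

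**2. Does the sample size depend on the period?** The plan's own figure is a 95% half-width slightly below 4.5% at a proportion of 50% with 500 per group. Check: 1.96 × √(0.5 × 0.5/500) = 4.38%. It reproduces, and no calendar period enters it.

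**3. Which gap readmissions can qualify?** A case is a readmission within 18 or 30 days of an index discharge, and under Participants index stays lie in the two windows.
- A May 2019 readmission needs an index discharge in April or May 2019. No such stay is included, so it is not a study readmission and cannot be the first one.
- For the 30-day outcome, a discharge on 2 December 2018 reaches 1 January 2019, and a discharge on 31 December 2018 reaches 30 January 2019. Qualifying gap readmissions therefore lie in about 1 to 30 January 2019: 30 days, not 265. For the 18-day outcome the stretch is shorter.

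**4. Size of what is left.** The documents give no repeat-readmission rate, so I assume Poisson readmissions at L per patient-year, with L from 0.05 to 0.5. The share of first readmissions in the 2019 window that changes status when d gap days are counted is 1 − exp(−L × d/365).

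| L | d = 265 (whole gap) | d = 30 (January 2019) |
|---|---|---|
| 0.05 | 3.6% | 0.4% |
| 0.1 | 7.0% | 0.8% |
| 0.25 | 16.6% | 2.0% |
| 0.5 | 30.4% | 4.0% |

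The d = 265 column would apply only if readmissions without an eligible index stay counted. The d = 30 column is itself generous, because only patients discharged in December 2018 can have a qualifying January readmission.

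For both windows pooled, the 2019 share of first readmissions is exp(−L)(1 − exp(−100L/365)) divided by that quantity plus (1 − exp(−L)).
- L = 0.05: 0.0129/(0.0129 + 0.0488) = 21%; 21% × 0.41% = about 0.1%.
- L = 0.5: 0.0776/(0.0776 + 0.3935) = 16.5%; 16.5% × 4.03% = about 0.7%.

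**5. Retrieval of the 30-day tails.** The last tails end on 30 January 2019 and 30 January 2020. The plan is dated 18.02.2020 ("Research plan, Version and date 18.02.2020, V4.0"), 19 days after the later one. The data could therefore already be retrieved, and no section says that capture stops on 31 December.

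**The case for a change.** The strongest opposing case is that the Abstract does not present its dates as outer limits; it says who will be included. Data collection gives no dates for the initial period, so the exclusion of January to September 2019 rests on Participants alone. With *study period* undefined, a reader could take it as the span from first to last date, and observed readmissions do feed calibration. If capture did stop on 31 December, an assumed even flow of discharges would lose roughly 7% to 15.5% of 30-day events in the 2019 window, depending on how soon readmissions occur.

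Part of this stands: the two date statements differ, and neither the study period nor the end of retrieval is written down. The consequences do not follow. Participants is the eligibility section, and its either/or wording cannot be read as a continuous span. Giving the first-readmission rule a 265-day reach means taking inclusion from Participants while importing the Abstract's period into a sentence of that same section. It also means counting readmissions that the outcome definition does not recognise. The truncation figure depends on a cut-off that the plan nowhere sets, whereas the outcome definition itself calls for the full 30 days.

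**Conclusion.** No change to the plan is needed. The date mismatch is a clerical slip in the Abstract: its dates are the first and last days of the two Methods windows. Correcting the sentence would be tidy but would alter no analysis. The undefined study period and the unstated end of retrieval are gaps that an analyst following Participants, Outcome(s) and Data collection would fill sensibly. Index stays come from the two windows, and each is followed for 18 or 30 days, into January where needed.

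What stays open is how a qualifying readmission in January 2019 bears on a later one by the same patient in the 2019 window. That concerns about 0.4% to 4.0% of first readmissions in that window and 0.1% to 0.7% pooled. These figures rest on the assumed Poisson rates and treat inclusion as going by discharge date; stays that straddle a boundary would shift the January dates slightly. Nothing here shows an effect on the ranking of the three models, and the precision target is untouched.

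### For the 18-day SwissDRG outcome, an unplanned readmission that did not lead to a case merging is classified inconsistently: in neither group, as a non-event, or as a case, depending on the section read

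*Combined protocol and SAP*

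**What the plan says.** All references are to the combined protocol and SAP.

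- **Participants, cases.** The 18-day case is "i) an unplanned readmission within 18 days according to SwissDRG's specifications". A separate item covers all-cause unplanned readmission within 30 days.
- **Participants, controls.** One sentence serves both outcomes: "The control group will consist of individuals who had no unplanned readmission within the relevant days after the index discharge".
- **Outcome(s), meaning of unplanned.** "An unplanned readmission will be defined as an urgent readmission, i.e. not scheduled in advance and requires treatment within 12 hours". Diagnostic category plays no part in this.
- **Outcome(s), secondary outcome.** This is an unplanned same-hospital readmission that led to a SwissDRG case merging. Records "are merged into a single case if they fall into the same major diagnostic category (MDC), occurred within 18 days" of the preceding discharge, and "are not excluded from the case merging rule".
- **Abstract.** "Cases will be inpatients that experienced an unplanned (all-cause) readmission within 18 or 30 days after the index discharge". Neither SwissDRG nor merging is mentioned. For controls: "The control group will consist of individuals who had no unscheduled readmission", with no time window.
- **Study design and Participants, eligibility.** All inpatients enter, subject to exclusions (a) to (h). An unmerged readmission is not among those exclusions.

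**The concern.** The 18-day case and control definitions are not complements. Cases are limited to readmissions that were merged; controls must be free of any unplanned readmission in the window. Take a patient discharged after a cardiac stay and readmitted urgently on day 7 with a fracture. The second stay is in a different diagnostic category, so it is not merged and the patient is not a case. The patient did have an unplanned readmission within 18 days, so is not a control either. A readmission in the same category that is exempt from the merging rule falls into the same gap.

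Two analysts could follow the text faithfully and build different 18-day datasets. One that drops these stays selects its comparison group on something unknown at discharge, when the score would be used. The choice also sets the 18-day event rate, against which calibration, the Brier score and net benefit are judged. The 18-day target is part (ii) of the main objective, and the Introduction links merging to hospital payment, so the point is not incidental.

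**Working it through.** **1. One patient, three classifications.** Apply each text to an urgent, unscheduled readmission to the same hospital by day 18 that was not merged.

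| Text applied | Result for the 18-day outcome |
|---|---|
| Participants case and control wording, with the merging definition in Outcome(s) | Not a case and not a control |
| Outcome(s), read as yes/no over all included stays | Non-event |
| Abstract | Case |

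For the 30-day outcome the same patient is a case in both the Abstract and the Methods, so nothing changes there.

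**2. The plan's own figure.** Sample size states a half-width slightly below 4.5% for 500 cases at a point estimate of 50%. Check: 1.96 × √(0.5 × 0.5 / 500) = 4.38%. It reproduces. The section does not say which outcome the 500 cases refer to.

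**3. Inputs for size.** The documents give no local readmission rate and no share of merged readmissions. Assumed: a 30-day unplanned rate of 5% to 15%, of which 70% occur by day 18, giving an 18-day rate of 3.5% to 10.5%; and 30% to 60% of those merged (same category and not exempt).

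**4. Denominator and event rate, per 10,000 included stays.** Let R be the readmitted, M the merged and U = R − M the unmerged. The event rate is M / (10,000 − U) if U is dropped, M / 10,000 if U are non-events, and R / 10,000 under the Abstract.

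| 18-day rate, merged share | M | U | U dropped | U non-events | Abstract |
|---|---|---|---|---|---|
| 3.5%, 30% | 105 | 245 | 1.08% | 1.05% | 3.5% |
| 3.5%, 60% | 210 | 140 | 2.13% | 2.10% | 3.5% |
| 10.5%, 30% | 315 | 735 | 3.40% | 3.15% | 10.5% |
| 10.5%, 60% | 630 | 420 | 6.58% | 6.30% | 10.5% |

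The unmerged are 1.4% to 7.35% of all stays. The Abstract's case count is 1/0.6 = 1.7 to 1/0.3 = 3.3 times the merged count; that ratio is simply the assumed share inverted.

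**5. AUC.** Assume an AUC of 0.70 for merged cases against stays with no unplanned readmission. Let w = U / (10,000 − M) be the unmerged share of non-events, and A the AUC of merged cases against unmerged readmissions. Keeping the unmerged as non-events gives (1 − w) × 0.70 + w × A, so dropping them raises the AUC by w × (0.70 − A).

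- Smallest w: 140 / 9,790 = 1.43%. Largest w: 735 / 9,685 = 7.59%.
- Unmerged score like merged (A = 0.50): 0.0143 × 0.20 = 0.003, up to 0.0759 × 0.20 = 0.015.
- Unmerged score lower than merged (A = 0.60): 0.0143 × 0.10 = 0.001, up to 0.0759 × 0.10 = 0.008.

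**6. Precision, conditionally.** If 500 cases were counted by the Abstract's definition, 150 to 300 would be merged cases. The worst-case half-width for sensitivity would be 1.96 × √(0.25/150) = 8.0% to 1.96 × √(0.25/300) = 5.7%, above the plan's 5% limit.

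**The case against.** The strongest reply is that the plan already implies the right answer. The study takes all inpatients, the exclusions are listed and do not mention unmerged readmissions, and the secondary outcome is a yes/no event. Brier score, decile calibration and net benefit are analyses of a binary outcome over a cohort. The control sentence follows directly after the two case definitions and can be taken as their complement. On that view the patient is a non-event. The Abstract is a compressed summary, and the objective, Participants and Outcome(s) all tie the 18-day outcome to SwissDRG.

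Much of this stands. A reader might infer that the plan definitely removes these patients, or that the 18-day rate has no denominator. The documents do not support either inference, because the non-event reading is available and all included stays would then be the denominator. What does not stand is that the text settles the matter: in the control sentence, the word relevant qualifies the days and not the type of readmission.

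A reader might also infer that the models' 18-day discrimination is shown to be inflated, or that their ranking would change. Neither is shown. The AUC range rests wholly on assumptions, and its upper end needs the highest assumed rate, the lowest assumed merged share and equal scores for merged and unmerged readmissions. With 500 cases and 500 controls, the Hanley-McNeil 95% half-width at an AUC of 0.70 is about 0.032, so even 0.015 is under half of it, although a larger cohort would narrow that interval. Nor does the precision calculation show that the study will be short of cases: 500 is a stated minimum and all eligible stays are taken.

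**Conclusion.** The inconsistency is real and rests on wording alone. For the 18-day outcome, an unmerged unplanned readmission is in neither group, a non-event or a case according to which text is applied, and no section resolves it. Using the control sentence as written would select the comparison group on a post-discharge event.

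Under the stated assumptions, dropping these stays rather than keeping them as non-events moves the event rate only slightly (at most from 3.15% to 3.40%, or 6.30% to 6.58%) and raises the AUC by roughly 0.003 to 0.015, or less if unmerged readmissions score lower than merged ones. Adopting the Abstract's definition would matter much more for the case count and event rate, but it is the less likely path for an analyst who has the Methods. The point is confined to the 18-day secondary outcome. It should be corrected before analysis, as a clarification and not as a fault that undermines the study.

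**What to change.** - **Participants.** Define the 18-day comparison group as every included index stay without an unplanned readmission leading to a SwissDRG case merging within 18 days. State explicitly that this includes stays followed by an unplanned readmission that was not merged, whether because of another diagnostic category or an exemption from the rule. Keep the present control wording for the 30-day outcome only.
- **Abstract.** Limit all-cause to the 30-day outcome and tie the 18-day outcome to SwissDRG case merging.
- **Optional.** Report 18-day all-cause readmission as a labelled sensitivity outcome. The gap closes without it.

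The cost is a few sentences, plus one table if the optional analysis is added. No new data are needed. The 18-day AUC may come out slightly lower than if the unmerged readmissions were dropped.
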